14.2. Pregnancy and In Utero Drug Exposure

The investigator will attempt to collect pregnancy information if a female patient or a male patient's female partner becomes pregnant while the patient is participating in this study. The pregnancy information will be recorded on the appropriate form and must be submitted to the Sponsor within 2 weeks of learning of the pregnancy. The patient or partner will be followed for the outcome of the pregnancy. Information on the status of the mother and child will be forwarded to the Sponsor or designee. Generally, follow up will be no longer than 6 to 8 weeks following the estimated delivery date. Any premature termination of the pregnancy will be reported.

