Each TD patient in the expansion cohort will have a defined "pre-transfusion hemoglobin threshold" which will be calculated based on transfusion history and will be used for determining when to transfuse during the study. The baseline pre-transfusion hemoglobin threshold will be the mean of all documented pre-transfusion hemoglobin values during the 12 weeks prior to C1D1. During treatment, if the pre-transfusion hemoglobin value is increased by \geq 1 g/dL compared to

the baseline pre-transfusion hemoglobin threshold for that patient, transfusion should be delayed by a minimum of 7 days and/or the number of units transfused should be reduced by 1 or more RBC units. Patients may be transfused at the investigator's discretion for symptoms related to anemia or other requirements (e.g., infection).

Cohort^a	ACE-536 Dose Level^b (mg/kg)	Number of Patients
1	0.2	3-6
2	0.4	3-6
3	0.6	3-6
4	0.8	3-6
5	1.0	3-6
6	1.25	3-6
7	1.5	3-6
Expansion	TBD	30 ^c
Planned Total (All Cohorts):		Approximately 51-72

^a Cohort escalation is based on SRT review and recommendation to enroll additional cohorts and/or the expansion cohort.

^b The ACE-536 Dose Level for cohort 1 is 0.2 mg/kg. The dose level indicated for all subsequent cohorts is the maximum dose level that can be recommended by the SRT for escalation per the modified Fibonacci dose escalation scheme.

^c The expansion cohort will consist of 30 patients, including a minimum of 12 patients who are non-transfusion dependent and a minimum of 12 patients who are transfusion dependent (including a minimum of 6 thalassemia major patients with onset of regular transfusions before age 4 years, and a minimum of 6 patients with onset of regular transfusions after age 4 years).

Maximum Number of Patients (Planned): 51-72 patients

Duration of Treatment: The total duration of participation for a patient is approximately 24 weeks (4 week screening period, 12 week treatment period, and 8 week follow up period). If a patient has a positive anti-drug antibody (ADA) result at the last visit, the patient may be asked to return for additional ADA testing every three months, until a negative result is obtained, or the result is considered to be stabilized.

Diagnosis and Main Criteria for Eligibility

Inclusion Criteria:

1. Men or women \geq 18 years of age.

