- ¹⁰ **Pregnancy** test (urine or serum) and menstrual history is required prior to C1D1 for female patients of child bearing potential only.
- ¹¹ Transfusion history will be collected for 12 months prior to C1D1.
- ¹² **End of Treatment (EOT):** Should be performed 28 days (\pm 7 days) after the last dose of ACE-536. Patients who discontinue treatment early should complete the end of treatment visit at the time of discontinuation and complete the Day 141 follow up visit 28 days (\pm 7 days) after the EOT visit.
- ¹³ **End of Study (EOS):** Should be performed 28 days (\pm 7 days) after the Day 113/EOT visit (56 days after the last dose of ACE-536).
- ¹⁴ **Day 85 \pm 2 days** is the last possible study day that ACE-536 may be administered, regardless of the cycle.
- ¹⁵ If a **dose delay** is required per the dose modification rules the patient will not be dosed. The patient will return weekly to assess hematology results and adverse events until the patient is eligible to administer the next dose of ACE-536.
- ¹⁶ If the patient has a positive ADA result at their last assessment, the patient may be asked to return approximately every three months for additional testing until a negative result is obtained or the result is considered stabilized.
- ¹⁷ MRI for liver iron content will be performed at selected sites.
- ¹⁸ For the first dose of ACE-536, dosing should occur after a minimum of 7 days post-transfusion; subsequent doses should not be given within 24 hours of transfusion or planned transfusion.
- ¹⁹ Administration of quality of life questionnaires, including but not limited to FACT-An and SF-36 is required for patients in the expansion cohort only.
- ²⁰ QoL questionnaires including but not limited to FACT-An and SF-36 should be completed at the EOT visit only for expansion cohort patients who discontinue treatment early.
- ²¹ Abdominal ultrasound of the spleen is required for patients with no prior splenectomy in the dose escalation cohorts only. Patients in these cohorts with clinical signs of a change in spleen size or abnormality should have an abdominal ultrasound as needed throughout study.
- ²² Pregnancy test is not required at Day 141/EOS.
- ²³ Physical exam should include an optional evaluation of gonadal size in males at C1D1, EOT, and EOS visits only.
- ²⁴ MRI of the chest and abdomen for EMH masses and spleen, DXA for BMD and 6MWT for NTD patients will be performed in the expansion cohort patients only, at selected sites.

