No reproductive toxicity studies have been conducted with ACE-536 and therefore ACE-536 should not be administered to pregnant women. Male and female subjects of childbearing potential participating in studies of ACE-536 must be willing to abstain from sexual intercourse or use adequate contraception during the treatment and for 12 weeks following the last dose of ACE-536. The effects of ACE-536 on the developing fetus are unknown. It is not known if ACE-536 is secreted in milk; therefore, ACE-536 should not be administered to nursing mothers.

It is unknown if humans will experience any of the effects of ACE-536 that were noted in the rat and monkey toxicology studies. Safety effects will be monitored closely through adverse event reporting, clinical laboratory tests, vital signs, and physical examinations.

A comprehensive review of ACE-536, as well as details regarding the information summarized above, is provided in the Investigator's Brochure (IB). The ACE-536 IB should be reviewed prior to initiating the study.

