9.3. Selection of Study Population

9.3.1. Inclusion Criteria

Eligible patients must meet **all** of the following criteria:

1. Men or women \geq 18 years of age.
2. For the dose escalation phase of the study: documented diagnosis of β -thalassemia intermedia (transfusion dependent patients must not have begun regular transfusions at age < 4.0 years)
For the expansion cohort: documented diagnosis of β -thalassemia (including β -thalassemia major or β -thalassemia intermedia).
3. Prior splenectomy or spleen size < 18 cm in the longest diameter by abdominal ultrasound (dose escalation cohorts only).
4. Anemia, defined as:
 - a. Mean hemoglobin concentration < 10.0 g/dL of 2 measurements (one performed within one day prior to Cycle 1 Day 1 and the other performed during the screening period [Day -28 to Day -1]) in non-transfusion dependent patients, defined as having received < 4 units of RBCs within 8 weeks prior to Cycle 1 Day 1, OR
 - b. Transfusion dependent, defined as requiring ≥ 4 units of RBCs every 8 weeks (confirmed over 6 months prior to Cycle 1 Day 1).
5. Aspartate aminotransferase (AST) or alanine aminotransferase (ALT) $< 3 \times$ upper limit of normal (ULN).
6. Serum creatinine $\leq 1.5 \times$ ULN.
7. Females of child bearing potential (defined as sexually mature women who have not undergone hysterectomy or bilateral oophorectomy, or are not naturally postmenopausal ≥ 24 consecutive months) must have negative urine or blood pregnancy test prior to enrollment and use adequate birth control methods (abstinence, oral contraceptives, barrier method with spermicide, or surgical sterilization) during study participation and for 12 weeks following the last dose of ACE-536. Males must agree to use a latex condom during any sexual contact with females of child-bearing potential during study participation and for 12 weeks following the last dose of ACE-536, even if he has undergone a successful vasectomy. Patients must be counseled concerning measures to be used to prevent pregnancy and potential toxicities prior to the first dose of ACE-536.
8. Patients are able to adhere to the study visit schedule, understand and comply with all protocol requirements.
9. Understand and able to provide written informed consent.

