12.2. Dosing Days and Interim Visits

- For the first dose of ACE-536, dosing should occur after a minimum of 7 days post-transfusion; subsequent doses should not be given within 24 hours of transfusion or planned transfusion.
- Note: For any RBC transfusions received during the study, collect hemoglobin value just prior to transfusion.
- Each TD patient in the expansion cohort will have a baseline “pre-transfusion hemoglobin threshold” which will be calculated based on transfusion history and will be used for determining when to transfuse during the study
- All screening and Cycle 1 Day 1 procedure results required to confirm eligibility must be obtained and reviewed prior to study drug administration. Patient eligibility must be confirmed from these results.
- A patient will be considered enrolled into the study once a multi-digit patient identification number has been assigned to the patient. After assignment of the patient identification number and the completion of the required procedures, study drug administration may occur. Note that the patient dose must be calculated based on the patient’s weight on the day of dosing.
- All study procedures on each dosing day must be done prior to administration of study drug.
- Patients should be observed for a minimum of 30 minutes following treatment with ACE-536.
- If a dose delay is required per the patient dose modification rules (see [Section 10.8.1](#)), the patient will not be dosed. The patient will return weekly for assessment of hematology results and adverse events until the patient is eligible to receive the next dose of ACE-536.
- The hematology results can be collected up to 24 hours prior to the dosing day. For Cycle 1 Day 1, the hemoglobin should be available to confirm eligibility within one day prior.
- Any non-serious AEs that occur prior to dosing on Cycle 1 Day 1 should be recorded in the Medical History CRF.
- All AEs that occur after dosing on Cycle 1 Day 1 should be recorded in the AE CRF.
- On subsequent dosing days, all AEs and abnormal findings that might require modification of dosing (see [Section 10.8](#)) should be reviewed prior to dosing to ensure that the patient is still eligible to receive additional doses of ACE-536.
- Pregnancy test (urine or serum) and menstrual history is required of female patients of child bearing potential only.
- Physical exam on Cycle 1 Day 1 should include an optional evaluation of gonadal size of male patients.

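### Protocol 14.2 stops collecting new pregnancies when participation ends, nominally 8 weeks after the last dose, although contraception is required for 12 weeks

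*Protocol*

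**What the plan says.** Protocol 7.4 reports that there are no reproductive toxicity data for the drug and adds: "The effects of ACE-536 on the developing fetus are unknown". It asks men and women to abstain or to "use adequate contraception during the treatment and for 12 weeks following the last dose of ACE-536". Inclusion criterion 7 (section 9.3.1) applies the requirement "during study participation and for 12 weeks following the last dose of ACE-536".

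Section 14.2 collects a pregnancy in a female patient, or where a male patient's "female partner becomes pregnant while the patient is participating in this study". The form is due within 2 weeks of the site learning of the pregnancy. The outcome is then followed, generally to no later than 6 to 8 weeks after the estimated delivery date.

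The synopsis divides participation into a "4 week screening period, 12 week treatment period, and 8 week follow up period". The schedule of events (footnote 13) puts EOS 56 days after the last dose. Sections 14.5 and 14.5.1 end the documentation of adverse events and serious adverse events at that same point.

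**The concern.** The collection rule is tied to participation, and the contraception rule to a longer fixed period after the last dose. A patient or partner who conceives after EOS but before week 12 is in a period when the protocol still asks for contraception, yet 14.2 does not ask the site to record the pregnancy. With no reproductive toxicity data, each pregnancy with possible exposure is scarce information. A site that follows the text as written could leave such a pregnancy and its outcome unrecorded.

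**Working it through.** **Inputs**
- Contraception after the last dose: 12 weeks = 84 days (Protocol 7.4; 9.3.1, criterion 7).
- Last possible dose: Day 85 (Protocol 10.1). End of Treatment (EOT): Day 113. EOS: Day 141 (schedule of events).
- EOT is 28 ± 7 days after the last dose, and EOS is 28 ± 7 days after EOT (footnotes 12 and 13).
- Early discontinuation: EOT at the time of stopping, EOS about 28 days later (footnote 12; section 9.4).

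**Step 1. Reproduce the plan's own figures.** Participation: 4 + 12 + 8 = 24 weeks, as stated. EOS after the last dose: 141 − 85 = 56 days = 8 weeks, as stated.

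**Step 2. Nominal gap.** 84 − 56 = 28 days, and 28 / 84 = 33.3%. These are weeks 9 to 12 after the last dose.

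**Step 3. Visit windows.**
- Earliest EOS: 21 + 21 = 42 days. Gap 84 − 42 = 42 days (50%).
- Latest EOS: 35 + 35 = 70 days. Gap 84 − 70 = 14 days (16.7%).

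**Step 4. Early discontinuation.** The documents do not say how long after the last dose a patient stops, so I assume 0 to 21 days (one dosing interval).
- Stop at day 0: EOS at 0 + 28 = 28 days. Gap 84 − 28 = 56 days (66.7%).
- Stop at day 21: EOS at 21 + 28 = 49 days. Gap 84 − 49 = 35 days (41.7%).
- With the ± 7 days on EOS, the extremes are 0 + 21 = 21 days (gap 63 days, 75%) and 21 + 35 = 56 days (gap 28 days, 33.3%).

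**Step 5. Could another rule close the gap?**
- *A wider meaning of participation.* Criterion 7 names participation and the 12 weeks as two separate periods, and the synopsis gives participation a length. Reading 14.2 as covering all 12 weeks is not supported.
- *Serious adverse event reporting.* A birth defect is a serious event under 14.1, but documentation ends 56 days after the last dose, and 14.7 requires notification only for events within the reporting period. A birth after a conception in weeks 9 to 12 would come months later.
- *Extension study.* SAP 3.3 lets some patients roll over directly and skip EOS. Those who complete EOS wait at least 28 days after it, nominally from day 56 to 56 + 28 = day 84, which is the same interval. Neither document says that the extension collects pregnancies for this study.
- *Extra antibody visits* are optional and only for patients with a positive result.

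**The case against.** The strongest reply is that the practical yield is small. The protocol plans 51 to 72 patients, all under contraception rules, and the documents give no basis for an expected number of missed pregnancies. Section 14.2 does not forbid reporting a later one, and some patients stay in contact through the extension study. The protocol sets a contraception duration; it does not define a fetal risk window or say that all 12 weeks carry equal risk. The one-third figure is therefore a share of calendar time, not of exposure or events. All of this stands and limits the weight of the point, but none of it brings weeks 9 to 12 within the collection rule.

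A reader might also infer four stronger things that the documents do not support:

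- *That detection stops at EOT.* Footnote 22 says: "Pregnancy test is not required at Day 141/EOS". But section 12.5 still collects menstrual history at EOS.
- *That a conception just before EOS, recognised afterwards, is lost.* Section 14.2 turns on when the pregnancy begins, and the 2-week deadline runs from when the site learns of it. Such a pregnancy is already covered.
- *That residual drug shows the uncovered weeks to be unsafe.* The half-lives in section 7.3 (15.5 to 18.5 days) are phase 1 means in healthy postmenopausal women at doses up to 0.25 mg/kg. The documents state no accepted residual level, and there is always more drug at an earlier time than at a later one.
- *That the schedule and section 12.2 contradict each other on a test at Cycle 1 Day 1.* The schedule marks none on that day. Footnote 10 asks for one beforehand, and criterion 7 for a negative result before enrolment. The bullet in 12.2, "Pregnancy test (urine or serum) and menstrual history is required of female patients of child bearing potential only", names no visit. This is an ambiguity at most, and separate from the collection gap.

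**Conclusion.** The mismatch holds on the text. New pregnancies are collected to a nominal 56 days after the last dose and contraception is required to 84 days, so 28 days (one third of the post-dose contraception period) are uncovered. The range is 14 to 42 days across the visit windows. For early discontinuers it is 35 to 56 days at the nominal EOS interval, if they stop 0 to 21 days after the last dose. The conclusion assumes that participation ends at EOS, as the synopsis and schedule indicate, and that no document outside these two extends collection. It concerns only pregnancies that begin after EOS; those that begin earlier are followed to outcome. This is a gap in safety data collection that is cheap to close. It has no bearing on the primary endpoint, power or any planned analysis.

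**What to change.** Reword 14.2 to collect any pregnancy, in a patient or a male patient's partner, that begins from the first dose through the end of the protocol's contraception period (currently 12 weeks after the last dose), with outcome follow-up as already described. Pregnancies that 14.2 already covers before the first dose should stay covered. Tying the rule to the contraception period, not to a fixed number of weeks, keeps the two aligned if that period changes. At the existing EOS visit, sites should tell patients to report a pregnancy that begins within that period.

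The cost is amendment wording and one instruction. The downside is an occasional pregnancy report after EOS. No visit or procedure is added, and the contraception requirement is unchanged.

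As a separate minor clarification, the schedule of events and section 12.2 should be reconciled on whether the pregnancy test applies at Cycle 1 Day 1. Which reading is intended is for the sponsor to state.

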14.3. Severity

Investigators must evaluate the severity/intensity of AEs according to the current active minor version of the National Cancer Institute Common Toxicity Criteria for Adverse Events, version 4.0 (NCI-CTCAE v4.0), preferentially using the graded scales. If there is a change in severity of an adverse event, it must be recorded as a separate event. If a particular AE's severity/intensity is not specifically graded, the investigator should apply the general guidelines for determination of Grade 1 through Grade 5 as listed in the NCI-CTCAE v4.0 cover page (as shown below), using their best medical judgment:

Grade 1: Mild; asymptomatic or mild symptoms; clinical or diagnostic observations only; intervention not indicated.

Grade 2: Moderate; minimal, local, or noninvasive intervention indicated; limiting age-appropriate instrumental activities of daily living (preparing meals, shopping for groceries or clothes, using the telephone, managing money, etc.).

Grade 3: Severe or medically significant but not immediately life-threatening; hospitalization or prolongation of hospitalization indicated; disabling; limiting self-care activities of daily living

(bathing, dressing and undressing, feeding self, using the toilet, taking medications, and not bedridden).

Grade 4: Life-threatening consequences; urgent intervention indicated.

Grade 5: Death related to AE.

14.4. Relationship to Study Drug

Investigators must also assess the causal relationship of each AE to ACE-536. Factors for the assessment of causal relationship include, but are not limited to, temporal relationship between the AE and the administration of ACE-536, known side effects of ACE-536, medical history, concomitant therapy, course of the underlying disease, and pertinent study procedures.

Probable: A causal relationship is clinically/biologically highly plausible and there is a plausible time sequence between onset of the AE and administration of ACE-536 and there is a reasonable response on withdrawal.

Possible: A causal relationship is clinically/biologically plausible and there is a plausible time sequence between onset of the AE and administration of ACE-536.

Unlikely: A causal relationship is improbable and another documented cause of the AE is most plausible.

Unrelated: A causal relationship can be definitively excluded and another documented cause of the AE is most plausible.

14.5. Documentation and Methods of Reporting of Adverse Events by Investigator

It is the responsibility of the Investigator to document all adverse events that occur during the study. Patients will be evaluated and questioned generally for AEs during the course of the study, starting at the signing of the informed consent. The Investigator must report in detail all adverse signs and symptoms which are either volunteered by subjects or observed during or following the course of investigational product administration on the appropriate CRF page. All non-serious AEs occurring after signing of the ICF until a patient is dosed on Cycle 1 Day 1 are to be documented on the medical history CRF. All AEs and SAEs occurring after the Cycle 1 Day 1 dose through 56 days after the last study drug administration (End of Study visit) are to be reported and documented on the AE CRF.

All AEs spontaneously reported by the patient and/or in response to an open question from study personnel or revealed by observation, physical examination, or other diagnostic procedures will be recorded on the AE CRF. Any clinically relevant changes in laboratory assessments, or other clinical findings as described in [Section 14.1](#), are considered AEs and must be recorded on the AE CRF. AEs are to be followed for resolution as described in [Section 14.6](#).

It is important that each AE report include a description of the event, duration (onset and resolution dates), severity, relationship with ACE-536, any other potential causal factors, any treatment given or other action taken (including dose modification or discontinuation of ACE-536) and outcome. In addition, serious AEs (SAEs) should be identified and the

appropriate seriousness criteria documented. AEs categorized as SAEs must also be documented using an SAE Report Form as described in [Section 14.5.1](#).

Specific guidance can be found in the CRF Completion Guidelines provided by the Sponsor or designee.

14.5.1. Documentation of Serious Adverse Events

All SAEs that occur after the first study drug administration on Cycle 1 Day 1 until 56 days after the last study drug administration (End of Study visit) are to be documented on the AE CRF. SAEs should not be reported for patients who are considered screen failures unless the event is deemed due to a protocol required procedure.

For all SAEs, an SAE form must be completed with as much information as possible and submitted within the time frame described in [Section 14.7](#).

When new significant information is obtained, as well as when the outcome of an event is known, the investigator should record the information on a new SAE form. If the patient was hospitalized, a copy of the discharge summary must be included as part of the patient medical file. In all instances, the investigator should follow up with patients until the outcome of the SAE is known.

